8.1.1 Clinical Laboratory

- Hematology: total white blood cell count, hemoglobin, and platelets.
- Coagulation profile: prothrombin time (PT) and partial thromboplastin time (PTT)
- Biochemistry: sodium, potassium, glucose, blood urea nitrogen, creatinine, Cystatin c, calcium, phosphate (inorganic), uric acid, total protein, albumin, bilirubin (total), alkaline phosphatase, aspartate transaminase, alanine transaminase, gamma-glutamyl transferase, lactate dehydrogenase, and creatine phosphokinase
- Vitamin D
- Urinalysis: dipstick for presence of blood, glucose, ketones, and protein

8.2 Efficacy Variables

- Mean annualised change in estimated glomerular filtration rate (eGFR_{CKD-EPI}) (See Appendix 6)
- Left Ventricular Mass Index (g/m^2) preferably by MRI (echocardiogram can be used as an alternative) (See Appendix 4)
- Plasma Lyso-Gb3
- Plasma Gb3
- Urine Lyso-Gb3
- Protein/Creatinine ratio spot urine test
- Frequency of pain medication use
- Exercise tolerance (Stress Test)
- Short Form Brief Pain Inventory (BPI) (See Appendix 7)
- Mainz Severity Score Index (MSSI) (See Appendix 5)

-
- Quality of life EQ-5D-5L (See Appendix 9)

8.3 Adverse Events

8.3.1 Adverse Events (AE) and Serious Adverse Events (SAE)

An adverse event (AE) is any untoward medical occurrence in a subject participating in a clinical trial. An adverse event can be any unfavorable and unintended sign, symptom or disease temporally associated with the use of the study medication, whether or not considered related to the study medication. AEs will be collected from the start of treatment until 30 days following the final visit dose. Any events occurring prior to treatment will be recorded on the medical history page with the event name and onset date and end date if not continuing. Pre-existing, known clinically significant conditions observed at screening should be recorded as medical history.

This definition also includes accidental injuries, reasons for any change in medication (drug and/or dose) other than planned titration, reasons for admission to a hospital, or reasons for surgical procedures (unless for minor elective surgery for a pre-existing condition). It also includes adverse events commonly observed and adverse events anticipated based on the pharmacological effect of the study medication. Any laboratory abnormality assessed as clinically significant by the Investigator must be recorded as an adverse event.

A treatment emergent adverse event is any adverse event occurring after start of study medication and within the time of residual drug effect, or a pre-treatment adverse event or pre-existing medical condition that worsens in intensity after start of study medication and within the time of residual drug effect.

Adverse events should be recorded as diagnoses, if available. If not, separate sign(s) and symptom(s) are recorded. One diagnosis/symptom should be entered per record.

Note that death is not an event, but the cause of death is. An exception is the event of sudden death of unknown cause. Note that hospitalization is not an event; however, the reason for hospitalization is. Procedures are not events; the reasons for conducting the procedures are. In general, only the reason for conducting the procedure will be captured as an adverse event. However, if deemed necessary by the Investigator, a procedure can be captured along with the reason for conducting the procedure.

An overdose or medication error is not an adverse event unless it is temporally associated with an unfavourable or unintended sign or symptom.

Each AE is to be classified by the investigator as serious or non-serious. A serious adverse event (SAE) is any untoward medical occurrence or effect that occurs at any dose:

- Results in death
- Is life-threatening (i.e., an immediate risk of death)

-
- Requires in-patient hospitalization or prolongation of existing hospitalization
 - Results in persistent or significant disability/incapacity
 - Is associated with a congenital anomaly/birth defect
 - Is an important medical event

An adverse event caused by an overdose or medication error is considered serious if a criterion listed in the definition above is fulfilled.

Important adverse events that may not result in death, may not be life-threatening, or do not require hospitalization may be considered serious when, based upon appropriate medical judgment, they may jeopardize the subject's safety or may require medical or surgical intervention to prevent one of the outcomes listed above.

Serious adverse events also include any other event that the investigator or sponsor judges to be serious or which is defined as serious by the regulatory agency.

The investigator is to report all directly observed adverse events and all adverse events spontaneously reported by the trial subject using concise medical terminology. In addition, each trial subject will be questioned about adverse events. The question asked will be "Since you began taking the study medication, have you had any health problems?"

8.3.2 Procedures for Assessing, Recording, and Reporting Adverse Events and Serious Adverse Events

Throughout the duration of the study, the Investigator will closely monitor each subject for evidence of drug intolerance and for the development of clinical or laboratory evidence of adverse events. All adverse events (expected or unexpected) which occur during the course of the study, whether observed by the Investigator or by the subject, and whether or not thought to be drug-related, will be reported and followed until resolution or until they become stable.

The description of the adverse event will include description of event, start date, stop date, intensity, if it was serious, relationship to test drug, change in test drug dosage, if the subject died, and if treatment was required.

Events will be coded to one of the following intensity categories below:

Severity	Definition
Mild	Awareness of signs or symptoms, but no disruption of usual activity
Moderate	Event sufficient to affect usual activity (disturbing)
Severe	Event causes inability to work or perform usual activities (unacceptable)

Events will be coded into one of the following causality categories as defined below:

Category	Definition
Unrelated	Clearly and incontrovertibly due only to extraneous causes, and does not meet criteria listed under possible or probable.
Unlikely	Does not follow a reasonable temporal sequence from administration. May have been produced by the subject's clinical state or by environmental factors or other therapies administered.
Possible	Follows a reasonable temporal sequence from administration, but may have been also produced by the subject's clinical state, environmental factors or other therapies administered.
Probable	Clear-cut temporal association with administration with improvement on cessation of investigational medicinal product or reduction in dose. Reappears upon rechallenge. Follows a known pattern of response to the investigational medicinal product.

Adverse events with the causality assessed as unrelated or unlikely are categorized as not related to study medication.

Adverse events with the causality assessed as possible or probable are categorized as related to study medication and are called adverse drug reactions.

All SAEs must be reported immediately (no more than 24 hours after becoming aware of the event) by entering the information about the event in the eCRF forms. The Sponsor's Medical Director and Safety Monitor will be notified of the event by the eCRF system. In the case that the eCRF system is not available, the Investigator must contact Medical Director ([name]) or Safety Monitor ([name]) to notify the Sponsor of the event.

8.3.3 Acute Kidney Injury

Episodes of Acute Kidney Injury (AKI) will be considered adverse events. AKI will be defined by a 1.5 fold or greater increase in serum creatinine from the immediately previous laboratory value and assessment by the investigator. The Protalix Medical Director will work with the investigator to ensure that such changes in renal function are thoroughly evaluated.

9. STUDY PROCEDURES AND FLOW CHART

Activity	Screening Period		Visits Treatment Period PRX-102 (Pegunigalsidase alfa)						
	Screening Visit (-3 Month)	Visit A (-2 Month) and B (-1 Month)	Visit 1	Visits 2, 4, 6, 8, 10, 12, 13, 15, 17, 19, 21, 23, 25, 26	Visits 3, 5, 9, 11	Visits 7, 20 (Months 3 and 9)	Visit 14 (Month 6)	Visits 16, 18, 22, 24	Visit 27 (Month 12)
Sign IC	x								
Assign screening number	x								
Medical history	x								
Demographics	x								
Alpha-galactosidase activity in plasma and leucocytes	x								
Historical serum creatinine	x								
Vital signs (blood pressure, pulse, temperature and respiration)	x		x	x	x	x	x	x	x
Body weight	x		x			x	x		x
Body height	x								
Physical examination	x		x			x	x		x
Concomitant medications (including pain and premedications)	x	x	x	x	x	x	x	x	x
Hematology	x		x			x	x		x
Biochemistry	x		x			x	x		x
Serum Creatinine and Cystatin C	x	x	x		x	x	x	x	x
Urinalysis - dipstick	x		x			x	x		x
Protein/Creatinine ratio spot urine test	x	x	x			x	x		x
HbsAg, HCV & HIV	x								
Serum pregnancy test (beta HCG)	x		x						

Activity	Screening Period		Visits Treatment Period PRX-102 (Pegunigalsidase alfa)						
	Screening Visit (-3 Month)	Visit A (-2 Month) and B (-1 Month)	Visit 1	Visits 2, 4, 6, 8, 10, 12, 13, 15, 17, 19, 21, 23, 25, 26	Visits 3, 5, 9, 11	Visits 7, 20 (Months 3 and 9)	Visit 14 (Month 6)	Visits 16, 18, 22, 24	Visit 27 (Month 12)
Urine Lyso Gb3 concentration	x		x			x	x		x
Plasma Lyso Gb3	x		x			x	x		x
Plasma Gb3	x		x			x	x		x
Anti PRX-102 Antibodies (IgG)			x		x	x	x		x
Electrocardiography (ECG)	x		x			x	x		x
Chest X-ray	x								
Cardiac function assessment (echocardiography and stress test)	x		x				x		x
Cardiac MRI			x						x
Inclusion/exclusion criteria	x								
Request for subject approval	x								
Enrolment approval		x ¹							
Mutation analysis			x						
PT, PTT	x								
C3, C4	x								
Vit D	x								
Short Form Brief Pain Inventory (BPI)			x			x	x		x
Brain MRI			x						x
Mainz Severity Score Index (MSSI)			x				x		x
EQ-ED-5L			x				x		x
PRX-102 infusion+clinical observation			x	x	x	x	x	x	x
Adverse event assessments		x	x	x	x	x	x	x	x

¹ After Visit B

9.1 Study Visits

9.1.1 Screening Visit S1 (3 Months \pm 7days before Visit 1)

The following procedures will be performed:

- Administration of informed consent
- Assign Screening number
- Medical history, including Fabry disease history
- Demographics
- Alpha-galactosidase activity in plasma and leucocytes
- Historical serum creatinine values
- Vital signs (blood pressure, pulse, temperature and respiration rate)
- Body weight and height
- Physical examination
- Concomitant medications , including review of pain medication and premedication
- Clinical laboratory
 - Hematology
 - Biochemistry
 - Serum Creatinine and Cystatin C
 - Urinalysis by dipstick
 - Spot urine test for proteinuria
 - HbsAg, HCV, HIV
 - Serum pregnancy test (beta HCG)
 - Vit D
 - PT, PTT
 - C3, C4
 - Urine Lyso Gb3 concentration
 - Plasma Lyso Gb3
 - Plasma Gb3
- Electrocardiogram
- Chest X-ray – an X-ray from the previous three months is acceptable
- Cardiac function assessment with echocardiography and stress test
- Review of inclusion and exclusion criteria
- Request subject approval

Schedule the patient for the next visit.

9.1.2 Visits A and B (2 and 1 Month \pm 7 days before Visit 1)

The following procedures will be performed:

- Clinical laboratory
 - Serum Creatinine and Cystatin C
 - Spot urine test for proteinuria
- Concomitant medications including review of pain medication and premedication
- Adverse event assessment

Final enrolment approval will be determined after Visit B.

Schedule the patient for the next visit.

9.1.3 Visit 1(±7Days)

The initial PRX-102 infusion will occur at this visit and will take place at the clinic and will continue every two weeks. Vital signs will be measured at every infusion.

The following procedures will be performed:

- Vital signs (blood pressure, pulse, temperature and respiration rate)
- Body weight
- Physical examination
- Concomitant medications, including review of pain medication and premedication
- Clinical laboratory
 - Hematology
 - Biochemistry
 - Serum Creatinine and Cystatin C
 - Urinalysis by dipstick
 - Protein/Creatinine ratio spot urine test
 - Serum pregnancy test (beta HCG)
 - Antidrug antibodies(pre-infusion) (PRX-102)
 - Mutation analysis
 - Urine Lyso Gb3 concentration
 - Plasma Lyso Gb3
 - Plasma Gb3
- Electrocardiogram
- Cardiac function assessment with echocardiography and stress test
- Cardiac MRI
- Mainz Severity Score Index
- Quality of Life EQ-5D-5L
- Short Form Brief Pain Inventory
- Adverse event assessment
- PRX-102 infusion
- Brain MRI

The following procedures will be performed after all infusions:

1. Patients will be observed clinically for a minimum of 2 hours after dosing.
2. Vital signs will be evaluated every 30 minutes for the first hour, then every hour and at the end of clinical observation, if the patient tolerates the infusion.
3. The injection site will be evaluated.

A follow up telephone call with the patient will be held the day after the first infusion.

Schedule the patient for the next visit.

9.1.4 Visits 2, 4, 6, 8, 10, 12, 13, 15, 17, 19, 21, 23, 25, 26 (± 3 Days)

Taper of premedication will start at Visit 2 and occur over the next two months at the investigator's discretion.

The following procedures will be performed:

- Vital signs (blood pressure, pulse, temperature and respiration rate)
- Concomitant medications, including review of pain medication and premedication
- Adverse event assessment
- PRX-102 infusion
- Post dosing clinical observation

Schedule the patient for the next visit.

9.1.5 Visits 3, 5, 9, 11 (± 3 Days)

Premedication tapering will complete by visit 5 (Appendix 8). The following procedures will be performed:

- Vital signs (blood pressure, pulse, temperature and respiration rate)
- Concomitant medications, including review of pain medication and premedication
- Serum Creatinine and Cystatin C
- Antidrug antibodies (pre-infusion) (PRX-102)
- Adverse event assessment
- PRX-102 infusion
- Post dosing clinical observation

Schedule the patient for the next visit.

9.1.6 Visits 7, 20 (± 7 days)

PRX-102 infusions continue every 2 weeks. At Visit 7 if infusions are tolerated, infusion duration can be decreased to 1.5 hours as described in Appendix 2

The post dosing clinical observation length can be shortened to 1 hour pending patient tolerability per investigator discretion and after Medical Monitor approval when the patient has reached a stable infusion duration. Vital signs will be measured every 30 minutes when post dosing observation is reduced to 1 hour.

The following procedures will be performed:

- Vital signs (blood pressure, pulse, temperature and respiration rate)
- Physical examination
- Body weight
- Concomitant medications, including review of pain medication and premedication
- Clinical laboratory
 - Hematology
 - Biochemistry
 - Serum Creatinine and Cystatin C
 - Urinalysis by dipstick
 - Protein/Creatinine ratio spot urine test
 - Urine Lyso Gb3 concentration
 - Plasma Lyso Gb3
 - Plasma Gb3
 - Antidrug antibodies (pre dose) (PRX-102)
- Electrocardiogram
- Short Form Brief Pain Inventory
- Adverse event assessment
- PRX-102 infusion
- Post dosing clinical observation

Schedule the patient for the next visit.

9.1.7 Visit 14 (± 7 days)

The following procedures will be performed:

- Vital signs (blood pressure, pulse, temperature and respiration rate)
- Body weight
- Physical examination
- Concomitant medications, including review of pain medication and premedication
- Clinical laboratory
 - Hematology
 - Biochemistry
 - Serum Creatinine and Cystatin C
 - Urinalysis by dipstick
 - Protein/Creatinine ratio spot urine test
 - Urine Lyso Gb3 concentration

- Plasma Lyso Gb3
- Plasma Gb3
- Antidrug antibodies (pre dose) (PRX-102)
- Electrocardiogram
- Cardiac function assessment with echocardiography and stress test
- Short Form Brief Pain Inventory
- Mainz Severity Score Index
- Quality of Life EQ-5D-5L
- PRX-102 infusion
- Adverse event assessment
- Post dosing clinical observation

Schedule the patient for the next visit

9.1.8 Visits 16, 18, 22, 24 (± 3 Days)

The following procedures will be performed:

- Vital signs (blood pressure, pulse, temperature and respiration rate)
- Concomitant medications, including review of pain medication and premedication
- Adverse event assessment
- Serum Creatinine and Cystatin C
- PRX-102 infusion
- Post dosing clinical observation

Schedule the patient for the next visit.

9.1.9 Visit 27 (± 7 days) or Premature Withdrawal

The following procedures will be performed:

- Vital signs (blood pressure, pulse, temperature and respiration rate)
- Body weight
- Physical examination
- Concomitant medications, including review of pain medication and premedication
- Clinical laboratory
 - Hematology
 - Biochemistry
 - Serum Creatinine and Cystatin C
 - Urinalysis by dipstick
 - Protein/Creatinine ratio spot urine test
 - Urine Lyso Gb3 concentration
 - Plasma Lyso Gb3

- Plasma Gb3
 - Antidrug antibodies(pre dose) (PRX-102)
- Electrocardiogram
- Cardiac function assessment with echocardiography and stress test
- Cardiac MRI
- Brain MRI
- Short Form Brief Pain Inventory
- Mainz Severity Score Index
- Quality of Life EQ-5D-5L
- PRX-102 infusion
- Adverse event assessment
- Post dosing clinical observation

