TEST PRODUCT(S), DOSE AND MODE OF ADMINISTRATION: During the first 3 months (Screening period), patients will be on agalsidase alfa according to their previous regimen (dose, frequency and rate of infusion). Upon confirmation of eligibility, patients will be switched to PRX-102 1 mg/kg, intravenously to be administered over 3 hours, every 2 weeks. After the first 2 months of treatment with PRX-102, infusion time may be reduced gradually to 1.5 hours pending patient tolerability, investigator evaluation, and Sponsor Medical Monitor/Director approval.

STUDY DURATION: Total 15 months, with 3 months Screening while on agalsidase alfa and 12 months Treatment on PRX-102, with the option to be enrolled in an extension study upon completion of this study.

DISCONTINUATION FROM TREATMENT:

Reasons for permanent discontinuation include the following:

- The subject experiences two or more Grade 3 toxicities or one or more Grade 4 toxicity considered by the investigator associated with PRX-102 treatment (CTCAE v. 4.03, 2010)
- The subject experiences progressive hypersensitivity or severe hypersensitivity that is not allayed with pre-treatment
- The subject requests to discontinue treatment
- The Investigator feels that it is not in the best interest of the subject to continue treatment and/or if the investigator believes that the subject can no longer be compliant with the requirements of the study

SAFETY ENDPOINTS:

Change from baseline in:

- Clinical laboratory tests
- Physical examination
- Assessment of the injection site
- Electrocardiogram
- Treatment-emergent adverse events
- Ability to taper off infusion premedication throughout the first 2 months of the study
- Requirement for use of premedication overall to manage infusion reactions
- Treatment-emergent anti-PRX-102 antibodies

EFFICACY ENDPOINTS:

- Mean annualised change in estimated glomerular filtration rate (eGFR_{CKD-EPI})

- Left Ventricular Mass Index (g/m^2) preferably by MRI (echocardiogram can be used as an alternative)
- Plasma Lyso-Gb3
- Plasma Gb3
- Urine Lyso-Gb3
- Protein/Creatinine ratio spot urine test
- Frequency of pain medication use
- Exercise tolerance (Stress Test)
- Short Form Brief Pain Inventory (BPI)
- Mainz Severity Score Index (MSSI)
- Quality of life EQ-5D-5L

STATISTICAL ANALYSIS:

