6.3.3 Removal of Subjects from Therapy or Assessment

Reasons for permanent discontinuation include the following:

- The subject experiences two or more Grade 3 toxicities or one or more Grade 4 toxicity considered by the investigator associated with PRX-102 (CTCAE v. 4.03, 2010)
- The subject experiences progressive hypersensitivity or severe hypersensitivity that is not allayed with pre-treatment
- The subject requests to discontinue treatment
- The Investigator feels that it is not in the best interest of the subject to continue treatment and/or if the investigator believes that the subject can no longer be compliant with the requirements of the study

For any discontinuation, the Investigator will obtain all the required details and document the date and the main reason for the premature termination. If the reason for discontinuation is an adverse event, the specific event or the main laboratory abnormality will be recorded in the eCRF. The Investigator will make thorough efforts to document the outcome. The Investigator will attempt to continue to follow the subject for the full duration of the study or at least for 90 days following discontinuation. If circumstances prevent the subject from completing all visits, every attempt will be made to complete all procedures listed in Section 9 for Visit 27.

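### The Premature Withdrawal procedure list includes a PRX-102 infusion with no exemption, which read literally contradicts permanent discontinuation (a minor, low-likelihood drafting error on patient safety)

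*Protocol*

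**What the plan says.** Protocol section 9.1.9 is headed "Visit 27 (± 7 days) or Premature Withdrawal". It contains one list, introduced as procedures to be carried out, and does not separate patients who complete from patients who withdraw. Among the items are "PRX-102 infusion" and "Post dosing clinical observation", and the antibody sample is labelled as a pre-dose sample.

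Section 6.3.3 sets the stopping rules, which the synopsis repeats under "Reasons for permanent discontinuation include the following". Two of the four listed reasons concern drug safety. One is "two or more Grade 3 toxicities or one or more Grade 4 toxicity considered by the investigator associated with PRX-102". The other is "The subject experiences progressive hypersensitivity or severe hypersensitivity that is not allayed with pre-treatment". The remaining two are the subject's own request and the investigator's judgement.

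Section 6.3.3 also says what happens next. The investigator tries to follow the subject for the whole study, or for at least 90 days after discontinuation. If the subject cannot complete all visits, "every attempt will be made to complete all procedures listed in Section 9 for Visit 27".

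**The concern.** The protocol tells the site to stop PRX-102 permanently and also sends the same patient to a list that includes a dose of PRX-102. Both instructions stand in section 6.3.3: the stopping rule, and the pointer to the Visit 27 list.

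Safety is the trial's primary objective, and the two drug-safety reasons identify the patients for whom another infusion would be most hazardous. The protocol's introduction already reports one Grade 3 hypersensitivity-related serious event of bronchospasm on PRX-102. A site that followed 9.1.9 to the letter would dose such a patient. A site that rightly withheld the dose would be departing from the written procedure list. Neither position is one a protocol should create.

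**Working it through.** No arithmetic applies, and the plan states no figure on this point. The check sets the relevant texts side by side and looks for an exemption.

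1. **Who is sent to the list.** The heading of 9.1.9 names Premature Withdrawal. Section 6.3.3 separately directs discontinued subjects who cannot complete all visits to the Visit 27 procedures, using the word *all*.

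2. **What the list asks for.** Two items depend on a dose: the infusion and the observation after it. The antibody sample does not, although its pre-dose label assumes one. The other items can be done off drug.

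3. **What discontinuation means.** The synopsis places the same reasons under discontinuation from treatment, so it is PRX-102 that stops, not only attendance at visits.

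4. **Whether the other route avoids the problem.** The first preference in 6.3.3 is continued follow-up through the study. Every visit list from Visit 1 onward (sections 9.1.3 to 9.1.9) includes a PRX-102 infusion, and none is marked as applying only to patients still on treatment. The protocol therefore has no off-drug visit schedule, and the gap is wider than 9.1.9.

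5. **Whether an exemption appears elsewhere.**
   - The flow charts in protocol section 9 and SAP section 4.2 mark the infusion at Visit 27 (Month 12). Neither has a Premature Withdrawal column. Each carries one footnote, about enrolment approval.
   - Section 7.4 on administration, Appendix 2 on infusion rate and Appendix 8 on premedication say nothing about a withdrawal visit.
   - Appendix 3 stops an infusion when signs of hypersensitivity appear and governs whether it may resume. It does not address a later visit after permanent discontinuation.

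6. **What was intended.** Section 8.1 provides antibody sampling at 1 and 3 months after the last infusion for patients who end treatment. The protocol thus foresees patients who are off drug. The list in 9.1.9 closely follows the one for Visit 14, a dosing visit, including the pre-dose label. The infusion at withdrawal looks like a carry-over from that template.

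Steps 1 to 5 establish the literal contradiction. Step 6 indicates that it is a slip and not a decision.

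**The case against.** The strongest reply is that no competent investigator would read the protocol this way. Discontinuation is called permanent, and a specific stopping rule should govern over a generic procedure list. Appendix 3 requires the infusion to stop at the first sign of hypersensitivity. Section 3.3 lets subjects withdraw at any time. The wording in 6.3.3 is best-effort. Since every visit list contains an infusion, the natural convention is that the infusion line applies only to patients still on drug.

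Most of this stands, and it is why the likelihood is low. It does not remove the conflict, because the convention is nowhere written and Appendix 3 does not reach the withdrawal visit.

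Three stronger readings are tempting, and the documents support none of them.

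- **That all four discontinuation reasons conflict equally.** A patient who has asked to stop is protected by section 3.3, and no procedure list can authorise an infusion against that request. The overlap that matters for safety is the two drug-safety reasons.
- **That the defect is peculiar to 9.1.9.** The other visit lists share it, so the correction has to cover follow-up visits as well.
- **That patients have been or will be re-dosed.** Nothing in either document shows this. No expected number of withdrawals is given from which a count could be built.

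A further objection is that barring the infusion at Premature Withdrawal would deny a last dose to someone leaving for a non-safety reason. That is true, but the protocol gives no purpose for such a dose. Finally, SAP section 7.5 reports that about 80% of patients had completed or discontinued by the interim analysis, so the practical benefit left within this trial may be small.

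**Conclusion.** The contradiction is real as written and concerns patient safety. It is minor and unlikely to lead to harm. Nothing in the analysis depends on it: no endpoint, analysis population, sample size, estimate or planned comparison changes. Patients who complete Visit 27 on treatment are unaffected.

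The conclusion rests on a literal reading of 9.1.9 and 6.3.3 together and on the absence of an exemption in the protocol and SAP. Site instructions outside these documents could already contain one. The size cannot be expressed as a number of infusions or a risk. It is best described as one unqualified dosing instruction in the withdrawal list, with the same gap in the visits used for follow-up after discontinuation.

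**What to change.** Make three short changes to the protocol, by amendment or clarification letter:

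- **Section 9.1.9:** state that the PRX-102 infusion and post-dosing observation are not performed at Premature Withdrawal, and that the antibody sample is still taken there, without its pre-dose label.
- **Section 6.3.3:** except the infusion and post-dosing observation from the Visit 27 procedures, and from any follow-up visit after permanent discontinuation of treatment.
- **Flow chart in section 9:** add a footnote to the infusion row saying the same.

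The SAP flow chart can stay as it is, since the SAP does not direct dosing. The cost is two clauses and one footnote, with no added visits or procedures.
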